**Step 1:**

```
proc mi data=example seed=74746759 nimpute=XX round=1 out=example_1;  
  mcmc impute=monotone;  
  var <baseline score> ..... <visit12 score>;  
run;
```

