#### 6.1.4. Handling of Dropouts or Missing Data

Any subject who prematurely withdraws from the study will have their last available data assigned to an analysis window as described in [Section 6.1.5](#).

For the primary efficacy endpoint of IGA score (Phase 2b/Cohort 2 only), the primary analysis will impute missing values using a regression-based multiple imputation model. This is a three step process.

1. The first step is to understand the pattern of missingness. In order to perform the multiple imputation, a monotone missing pattern has to be achieved. For example, if there exist values for baseline, Week 8, and Week 12 visits, but missing values for the Week 2 or 4 visits, the Markov-Chain Monte-Carlo (MCMC) method will be used to impute the small amount of missing data that may be missing at the intermediate visits that is required to make the missing data pattern monotone before applying the multiple imputation algorithm. This method uses a non-informative Jeffreys prior to derive the posterior mode from the expectation-maximization (EM) algorithm as the starting values for the MCMC method. MCMC method will use seed of 74746759. The IGA score will be treated as a continuous variable for this step. To avoid values that could not be observed in practice, imputed values will be constrained to be integers in the range of 0 to 4.
  - a. The table below will determine the number of datasets to be imputed in this step. Determine the proportion of datapoints with non-monotone pattern across all visits and subjects which could be derived as a percentage of number of nonmonotone data points/total number of expected data points.

This can be determined as  $\frac{\text{number of non monotone visits}}{\text{total number of visits across all subjects}} * 100$

Non-monotone Missing Data	Number of Imputed Datasets
≤ 2%	1
> 2% to ≤ 5%	3
> 5%	10

2. Once the monotone pattern is achieved, the [next step](#) is to implement the imputation algorithm. For this, the Predictive Mean Matching method (PMM) will be used. This method is particularly helpful if the normality assumption is violated. For subjects with complete data up to a particular visit, a PMM model will be fit that includes the outcome at that visit as the dependent variable and as independent variables, IGA score outcomes at previous visits, treatment group, and pooled site group using a seed of 88734121. This process will be repeated 25 times, resulting in a total of 25 to 250 complete analysis

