datasets, depending on the number of imputed monotone datasets that are required. The seed or number of imputed datasets may be changed after unblinding in case of any issues with the imputation process, and it will be documented in the CSR if any change is required.

3. For each completed dataset, compute the necessary derived variables. The dichotomous success rate (clear or almost clear) will be derived. The results obtained will be analyzed using the CMH analysis for each of the complete analysis data sets stratified by baseline IGA score and site. The results will be combined into one multiple imputation inference (odds ratio, associated CI, and *P* value) using PROC MIANALYZE as illustrated below (Ratitch 2013).

This approach to imputation should be superior to other strategies such as carrying forward the last available observation, which may yield unrealistic imputed values. Also, the use of multiple imputation avoids the problem of artificially increasing power through data imputation associated with single-imputation methods because it accounts for the uncertainty associated with the imputation. Other missing data will not be imputed, with the exception of incomplete dates as described in Section 6.1.8. For responder analyses, missing data will be treated as a nonresponse with the exception of IGA. Only observed data will be summarized using descriptive statistics.

The SAS pseudo code for the multiple imputation process is listed below:

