3 = Moderate	XX (XX.X%)	XX (XX.X%)	XX (XX.X%)
4 = Severe	XX (XX.X%)	XX (XX.X%)	XX (XX.X%)
IGA Score of “Clear” or “Almost Clear” [1]			
Yes	XX (XX.X%)	XX (XX.X%)	XX (XX.X%)
90% CI [2]	(X.XX, X.XX)	(X.XX, X.XX)	(X.XX, X.XX)
95% CI [2]	(X.XX, X.XX)	(X.XX, X.XX)	(X.XX, X.XX)
No	XX (XX.X%)	XX (XX.X%)	XX (XX.X%)
Odds Ratio (90% CI) [3]	X.XX (X.XX, X.XX)	X.XX (X.XX, X.XX)	X.XX (X.XX, X.XX)
Odds Ratio (95% CI) [3]	X.XX (X.XX, X.XX)	X.XX (X.XX, X.XX)	X.XX (X.XX, X.XX)
P value [3]	X.XXXXX	X.XXXXX	X.XXXXX

*Continue for Weeks 4, 8, 12, and 13.*

Abbreviations: CI = confidence interval; IGA = investigator global assessment.

Note: The grades and success scores were summarized using observed dataset. The odds ratio and P values were summarized using multiple imputation dataset. Separate multiple imputation steps were used for monotone and non-monotone missing data. For monotone missing pattern, a predictive mean matching model was used to impute missing value for a subject at particular visit having IGA score at previous study visit, treatment group, and pooled site group as independent variables and outcome at study visit as dependent variable. For non-monotone missing IGA values, Markov-Chain Monte Carlo (MCMC) method was used to impute the data at intermediate visits to make the missing data pattern into monotone before applying the predictive mean matching multiple imputation algorithm. Percentages are n/Number of subjects in the ITT population within planned treatment at each visit\* 100. Baseline is the last non-missing measurement taken on or before the day of first application of study drug.

[1] IGA Score of “Clear” or “Almost Clear” (“Yes”) is defined as an IGA score of “Clear” or “Almost Clear”; “No” otherwise.

[2] 90% and 95% CIs for “Yes” are obtained using Wilson method.

[3] The odds ratio, 90% and 95% CIs, and P value are obtained from Cochran Mantel Haenszel test (stratified by pooled site group and baseline IGA grade) comparing: ARQ-252 cream (all strengths/dose frequencies) vs vehicle cream (all dose frequencies) and ARQ-252 cream 0.3% (all dose frequencies) vs vehicle cream (all dose frequencies).

Table 14.2.1.2.1  
Cohort 2: Summary of Investigator Global Assessment (IGA) Grades and Score of “Clear” or “Almost Clear” by Study Visit – Observed Data  
Categorical Results  
ITT Population

(Same shell as Table 14.2.1.1.1; use the below footnotes)

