Cohort 2: Summary and Change from Baseline in Investigator Global Assessment (IGA) Grades by Study Visit – Multiple Imputation  
ITT Population

Study Visit Statistic	Cohort 2		
	ARQ-252 Cream 0.3% QD (N=XX)	Change	ARQ-252 Cream 0.3% BID (N=XX)
	Observed	Change	Observed
Baseline			
n	XX		XX
Mean (SD)	XX.X (X.XX)		XX.X (X.XX)
Median	XX.X		XX.X
Min, Max	XX, XX		XX, XX
Q1, Q3	XX.X		XX.X
Week 2			
n	XX	XX	XX
Mean (SD)	XX.X (X.XX)	XX.X (X.XX)	XX.X (X.XX)
Median	XX.X	XX.X	XX.X
Min, Max	XX, XX	XX, XX	XX, XX
Q1, Q3	XX.X	XX.X	XX.X
Week 4			
n	XX	XX	XX
Mean (SD)	XX.X (X.XX)	XX.X (X.XX)	XX.X (X.XX)
Median	XX.X	XX.X	XX.X
Min, Max	XX, XX	XX, XX	XX, XX
Q1, Q3	XX.X	XX.X	XX.X

**Repeat this page for the remaining study drugs (ARQ-252 Cream 0.1% QD, Vehicle Cream (All Dose Frequencies)), showing the same study visits shown here. Then continue for Weeks 8, 12, and 13.**

Abbreviations: BID = twice daily; IGA = investigator global assessment; QD = once daily; SD = standard deviation.  
Note: Separate multiple imputation steps were used for monotone and non-monotone missing data. For monotone missing pattern, a predictive mean matching model was used to impute missing value for a subject at particular visit having IGA score at previous study visit, treatment group, and pooled site group as independent variables and outcome at study visit as dependent variable. For non-monotone missing IGA values, Markov-Chain Monte Carlo (MCMC) method was used to impute the data at intermediate visits to make the missing data pattern into monotone before applying the predictive mean matching multiple imputation algorithm. Subjects are summarized by averaging results over all imputed datasets within a subject before summarizing by planned treatment. IGA is a static qualitative evaluation of overall chronic hand eczema severity involving an ordinal scale with 5 severity grades (reported only in integers of 0 to 4) where 0 = Clear; 1 = Almost Clear; 2 = Mild; 3 = Moderate; 4 = Severe. Baseline is the last non-missing measurement taken on or before the day of first application of study drug. Change from baseline is calculated as result – baseline result.  
Reference Listing: 16.2.6.1

Table 14.2.1.5.2  
Cohort 2, Pooled Treatments: Summary and Change from Baseline in Investigator Global Assessment (IGA) Grades by Study Visit – Multiple Imputation  
ITT Population

Study Visit Statistic	Cohort 2			

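### Step 1 of the IGA multiple imputation leaves out treatment, two descriptive MI tables understate the SD, and Week 13 has no imputation model; the Week 12 primary is practically unaffected

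*SAP*

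**What the plan says.** **Step 1.** SAP 6.1.4 uses MCMC to "impute the small amount of missing data that may be missing at the intermediate visits", so that the remaining missing pattern is monotone. The prose names no covariates, and it adds that "imputed values will be constrained to be integers in the range of 0 to 4". The pseudo code is "proc mi data=example seed=74746759 nimpute=XX round=1 out=example_1" with "var <baseline score> ..... <visit12 score>". It has no treatment variable, no BY statement, no minimum and no maximum.

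**Step 2.** Predictive mean matching (PMM) fills the monotone tail from "IGA score outcomes at previous visits, treatment group, and pooled site group using a seed of 88734121". The Step 2 code also contains treatment and site. Its score list ends at visit 12 as well.

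**Week 13.** SAP 2.2.1.2 and 8.2.1 make Week 13 IGA results secondary endpoints and plan them on imputed and nonimputed data. The MI table shells carry the instruction "Continue for Weeks 4, 8, 12, and 13".

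**Descriptive MI tables.** The footnote to Tables 14.2.1.5.1 and 14.2.1.5.2 reads "Subjects are summarized by averaging results over all imputed datasets within a subject before summarizing by planned treatment". SAP 6.1.4 states "Only observed data will be summarized using descriptive statistics", while SAP 8.2.1 plans descriptive summaries of IGA change on imputed as well as nonimputed data.

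**The concern.** An imputation model that leaves out treatment draws each missing score from a distribution averaged over the arms. Imputed active scores drift up and imputed vehicle scores drift down, so the estimated difference shrinks. The MI shell footnotes repeat the same split, with covariates for the PMM step and none for the MCMC step, so the omission looks planned and not like a typing slip. Intermittent gaps are also foreseeable: SAP 6.2 expects visits missed because of COVID-19 and does not allow IGA to be done remotely.

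Averaging a subject's imputations replaces each missing score by something close to its predicted mean. The spread of the imputed values is lost, and that spread is the reason SAP 6.1.4 gives for using multiple imputation.

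The other two items are gaps between parts of the plan. A programmer following the code would not apply the stated bound, and would find no instruction for Week 13.

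**Working it through.** **1. The plan's own figure.** Step 1 yields 1, 3 or 10 datasets and Step 2 repeats 25 times: 1 × 25 = 25, 3 × 25 = 75, 10 × 25 = 250. This reproduces the stated range of 25 to 250.

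**2. Which step imputes Week 12.** Both score lists end at visit 12. A missing Week 12 score therefore has no later score in the model and always belongs to the monotone tail. Step 1 never imputes it. Step 2 does, with treatment and site in the model and with observed Week 12 scores as donors, which lie within 0-4. Step 1 can reach the primary only indirectly, through filled interim scores used as predictors.

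**3. Effect of leaving treatment out of Step 1.** A simulation used:
- 61 active and 62 pooled vehicle subjects (31 + 31, protocol 6.1.1), and 10% dropout (protocol 6.1.1);
- baseline IGA 20% mild, 60% moderate, 20% severe (the protocol caps mild and severe at 20% each);
- *assumed* IGA paths, giving a full-data Week 12 rate difference of about 0.31-0.33 (the protocol assumes 45% - 15% = 30 points);
- *assumed* intermittent gaps of 2%, 5% and 10% at Weeks 2, 4 and 8.

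There were 300 trials per setting with 5 imputations each. Bias is the MI rate difference minus the full-data rate difference in the same trials.

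| Visit | Gaps | Step 1 as coded | With treatment and 0-4 bound |
|---|---|---|---|
| Week 8 | 2% | 0.2687 - 0.2710 = -0.002 | 0.2741 - 0.2755 = -0.001 |
| Week 8 | 5% | 0.2663 - 0.2745 = -0.008 | 0.2731 - 0.2739 = -0.001 |
| Week 8 | 10% | 0.2660 - 0.2757 = -0.010 | 0.2705 - 0.2726 = -0.002 |
| Week 12 | 2% | 0.3114 - 0.3115 = -0.000 | 0.3109 - 0.3122 = -0.001 |
| Week 12 | 5% | 0.3119 - 0.3135 = -0.002 | 0.3158 - 0.3181 = -0.002 |
| Week 12 | 10% | 0.3236 - 0.3259 = -0.002 | 0.3087 - 0.3116 = -0.003 |

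The simulation standard error at Week 12 was about 0.0014; none was computed for Week 8. The worst Week 8 case is 0.0097 / 0.2757 = 3.5% of the effect. Limits: two arms instead of five, site omitted, MCMC approximated by chained normal regressions, treatment and bound switched on together, and only Week 8 tabulated among the interim visits. Weeks 2 and 4 share the mechanism, but no figure is claimed for them.

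**4. The bound.** About 2% of Step 1 draws rounded to a value outside 0-4 under these assumptions. A value of -1 falls on the same side of the clear/almost clear cut as 0, and 5 on the same side as 4, so responder status at that visit cannot flip. Such values can enter the numeric IGA change analyses at interim visits.

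**5. SD after averaging.** Let *f* be the missing fraction and *r* the correlation of a missing score with its predictors. After averaging many imputations, the missing part contributes variance r²σ² instead of σ². The SD ratio is therefore √[(1 - f) + f r²] = √[1 - f(1 - r²)].

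| f | r = 0.4 | r = 0.6 | r = 0.8 |
|---|---|---|---|
| 5% | 0.979 | 0.984 | 0.991 |
| 10% | 0.957 | 0.968 | 0.982 |
| 20% | 0.912 | 0.934 | 0.963 |

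For example, at f = 0.10 and r = 0.6: √(1 - 0.10 × 0.64) = √0.936 = 0.968. The SD is 2-4% too small at 10% missing and 1-9% too small over 5-20%. The values of *r*, and of *f* other than 10%, are assumptions. A separate simulation with 25 PMM imputations agrees: 0.974 / 1.016 = 0.959 at 10% missing and 0.930 / 1.010 = 0.921 at 20%.

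**The case against.** The strongest reply is that these are small matters in secondary or descriptive output. Step 1 is meant for a small amount of data. SAP 4.1 limits formal testing to the primary endpoint and HECSI change and percent change, with other P values for information only. Nonimputed versions of the same IGA analyses are planned, including observed-data Tables 14.2.1.5.3 and 14.2.1.5.4. The averaging is disclosed in the footnotes. All of this stands, and it limits the weight of the point.

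It also rules out several stronger inferences that a reader might draw:
- *The primary result is biased.* It is not in any practical sense: Step 1 does not impute Week 12, and the simulated change is within 0.003.
- *The plan has no 0-4 bound.* The prose states it. The mismatch is with code that the SAP itself calls pseudo code.
- *Week 13 MI results will be observed-case results under a wrong label.* The documents do not say what will be done, so Week 13 is unspecified. In the responder shells, counts and percentages are observed data by design, and only the odds ratio, its interval and the P value use MI.
- *Imputed descriptive tables break the plan.* SAP 8.2.1 provides for them; the general sentence in 6.1.4 does not. The two need reconciling.

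The reply does not answer two things: there is no reason to include treatment in one step and leave it out of the other, and an SD taken after averaging is too small by construction.

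**Conclusion.** The point holds as a set of modest corrections. Leaving treatment out of Step 1 slightly attenuates imputed-data secondary results at interim visits: about 0.002 to 0.010 on the Week 8 rate difference at 2-10% gaps, most of which disappears when treatment and the bound are added. The SDs in Tables 14.2.1.5.1 and 14.2.1.5.2 are about 2-4% too small at 10% missing; the quartiles come from the same averaged values. Neither the CMH nor the ANCOVA inference uses those SDs. The missing bound is a prose-code mismatch, and Week 13 is a gap in specification. It would go too far to call the IGA results wrong, or to treat the primary comparison as compromised.

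The sizes rest on assumed IGA paths, assumed intermittent missingness and assumed correlations; the documents give only the 10% dropout rate. The directions do not depend on those values.

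**What to change.** (a) **Step 1:** run it by treatment group (vehicle pooled) or add treatment indicators, and add minimum=0 maximum=4 so that the code matches the prose.

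(b) **Tables 14.2.1.5.1 and 14.2.1.5.2:** compute each statistic within each imputed dataset and then combine, or show observed data only. Reword SAP 6.1.4 so that its rule on descriptive statistics agrees with 8.2.1 and the table footnotes.

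(c) **Week 13:** either limit the MI tables to Week 12 and label Week 13 as observed data, or impute Week 13 in a way that leaves the Week 12 imputation unchanged, for example in a separate run. Do not simply extend both variable lists. A subject who missed Week 12 but attended Week 13 would then have an intermittent gap, and the primary score would come from a rounded normal draw in Step 1, without site (and without treatment unless (a) is done), instead of from PMM. It would also borrow from a visit one week after treatment ends.

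The cost is a few lines of code and some SAP wording. It should be done before unblinding, because SAP 6.1.4 provides for later changes only to the seed or the number of datasets.

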**Step 2:**

```
proc mi data=example_1 seed=88734121 nimpute=XX out=example_2;  
  class <treatment> <site>;  
  monotone regpmm(<baseline score> ..... <visit12 score>);  
  var <treatment> <site> <baseline score> ..... <visit12 score>;  
run;
```

XX will be the determined based on the proportion of missing data across visits.

**Step 3:** This step involves running CMH test stratified by baseline IGA score and site on each completed dataset and combining the results using PROC MIANALYZE.

```
proc freq data=example noprint;  
  by <imputationnumber> <visit> ;  
  tables <site> * <BL IGA> * <treatment> * <outcome> / cmh alpha=0.1;  
  output out=example_stat cmh;  
run;
```

In order to apply PROC MIANALYZE, normalizing transformations have to be applied to odds ratio. *P* values are obtained using Wilson Hilferty transformation as illustrated (Ratitch 2013).

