### Categorical Data Analysis

The primary efficacy endpoint is the rate of subjects achieving an IGA score of “Clear” or “Almost Clear” at Week 12.

The primary statistical comparisons for Cohort 2 subjects will be as follows:

- ARQ-252 cream 0.3% BID versus vehicle cream (all dose frequencies)
- ARQ-252 cream 0.3% QD versus vehicle cream (all dose frequencies)
- ARQ-252 cream 0.1% QD versus vehicle cream (all dose frequencies)
- ARQ-252 cream (all strengths and dose frequencies) versus vehicle cream (all dose frequencies)
- ARQ-252 cream 0.3% (all dose frequencies) versus vehicle cream (all dose frequencies)

The primary endpoint will be analyzed using a CMH test stratified by pooled study site group and baseline IGA category. Statistical significance will be concluded at the 10% significance level (2-sided) or less, as discussed in [Section 4.1](#). Odds ratios and 90% and 95% CIs for the odds ratios will be provided. Additionally, the 90% and 95% Wilson CIs for proportion of successes in each treatment group will be presented.

For the primary analysis, missing IGA scores will be imputed using multiple imputation as described in [Section 6.1.4](#). These imputations will result in a minimum of 25 to a maximum of 250 complete analysis datasets, depending on the number of imputed monotone datasets required. The CMH analyses will be performed separately for each of the complete analysis data sets, and the results will be combined into one multiple imputation inference (estimated treatment effect and associated CI and *P* value).

The primary efficacy analysis will be based on Cohort 2 subjects in the ITT population.

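### In SAP 6.1.4 the Step 2 imputation code and its XX sentence contradict the prose for the primary analysis: no BY on the Step 1 imputation number, and a count that is not 25

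*SAP*

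**What the plan says.** SAP 6.1.4 describes the imputation of missing IGA scores in prose and then in SAS pseudo code.

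**Prose.** Step 1 uses MCMC to fill intermittent gaps so that the pattern becomes monotone. On the count: "The table below will determine the number of datasets to be imputed in this step". The table gives 1 dataset when non-monotone points are at most 2%, 3 when above 2% and up to 5%, and 10 above 5%. Step 2 then applies predictive mean matching: "This process will be repeated 25 times, resulting in a total of 25 to 250 complete analysis" datasets. SAP 8.1.1 repeats the range ("These imputations will result in a minimum of 25 to a maximum of 250 complete analysis datasets") and adds: "The CMH analyses will be performed separately for each of the complete analysis data sets".

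**Pseudo code.**
- Step 1: "proc mi data=example seed=74746759 nimpute=XX round=1 out=example_1" with "mcmc impute=monotone". It writes XX stacked datasets to `example_1`.
- Step 2: "proc mi data=example_1 seed=88734121 nimpute=XX out=example_2". It reads that stack, and the only further statements are CLASS, MONOTONE and VAR.
- The one definition of XX follows Step 2: "XX will be the determined based on the proportion of missing data across visits". The number 25 appears nowhere in the code.
- Step 3 runs PROC FREQ with a BY on imputation number and visit, but its input is `example`, the name of the Step 1 input.

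**The concern.** The prose needs Step 2 to work inside each Step 1 dataset. Without a BY, Step 2 treats the whole stack as one dataset, so with 3 or 10 Step 1 datasets every subject appears 3 or 10 times. If that output is analysed by the Step 2 imputation number alone, the copies count as independent subjects and the standard error of the log odds ratio shrinks. The XX sentence raises a second problem: read literally for Step 2, the count becomes 1, 3 or 10 instead of 25, and 1 is single imputation.

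This is the primary analysis, tested at two-sided 10% in five comparisons (SAP 8.1.1) without multiplicity adjustment (SAP 6.1.3), and the same imputation feeds secondary IGA analyses (SAP 8.2.1). SAP 6.1.4 also lets the seed or the number of imputed datasets be changed after unblinding if the imputation runs into problems. The number of datasets is exactly what the code and the prose disagree on, so it should be settled before unblinding.

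**Working it through.** **1. The plan's own total.** Step 1 count × 25:

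- 1 × 25 = 25
- 3 × 25 = 75
- 10 × 25 = 250

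This reproduces the stated 25 to 250. The total is reached only if Step 2 runs 25 times within each Step 1 dataset.

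**2. The literal code.** Take XX from the table in both steps. Step 2 then yields 1, 3 or 10 imputation numbers, each holding k = 1, 3 or 10 copies of every subject. With 215 subjects (SAP 3.1) that is 215, 645 or 2,150 rows per imputation number.

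**3. Effect of stacking, by formula.** If k near-identical copies are analysed as one dataset, the variance is about 1/k of the correct value. The standard-error ratio is 1/√k, and the type I error at nominal two-sided 0.10 is 2 × [1 − Φ(1.645/√k)].

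| k | SE ratio | Type I error |
|---|---|---|
| 1 | 1.00 | 0.10 |
| 3 | 0.58 | 0.34 |
| 10 | 0.32 | 0.60 |

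**4. Effect of stacking, by simulation.** The formula ignores differences between the copies. The simulation compared 61 active with 62 pooled-vehicle subjects (31 + 31) under a null of 15% in both groups, with 10% and 20% dropout. It used predictive mean matching, the Mantel-Haenszel log odds ratio and Rubin's rules, with about 150 runs per case. Ranges cover both dropout rates and both Step 2 counts tried (XX, and a larger fixed count: 25 for k = 3, 10 for k = 10).

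| k | SE ratio, no BY | Type I error, no BY |
|---|---|---|
| 3 | 0.59-0.62 | 0.28-0.35 |
| 10 | 0.38-0.44 | 0.47-0.50 |

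With imputation done within each Step 1 dataset, type I error was 0.06-0.11 across all cases. That reference used 20 to 25 completed datasets in total, not the full 75 or 250 for k = 3 and 10. The Monte Carlo standard error is √(0.1 × 0.9/150) ≈ 0.025 near 0.10 and √(0.5 × 0.5/150) ≈ 0.04 near 0.50. For k = 10 the simulation therefore falls short of the formula's 0.60, and 47-60% is the fair range.

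**5. At most 2% non-monotone (k = 1).** With 25 Step 2 imputations, leaving out the BY gave a standard-error ratio of 1.00, so it has no effect. With XX = 1 there is no between-imputation variance to pool. The ratio was then 0.95 at 10% dropout and 0.91 at 20%. The matching type I errors, 0.09 and 0.15, are too noisy at this number of runs to carry weight.

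**6. How many points reach the 2% cut-off.** The documents do not fix how many visits count, so this is an assumption. With 4 visits, 0.02 × 215 × 4 = 17.2 points; with 5 visits, 0.02 × 215 × 5 = 21.5. About 18 to 22 intermittently missing IGA scores would move the trial to k = 3.

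**The case against.** The strongest reply is that the block is labelled pseudo code, is full of placeholders, and sits beside prose that is correct in two places. The prose limits the 1/3/10 table to Step 1, fixes 25 repeats, and requires a CMH analysis per completed dataset. It also says multiple imputation was chosen to avoid the false precision of single imputation, so XX = 1 in Step 2 would defeat the stated purpose. The XX sentence can be read as the Step 1 rule only. All of this stands: a programmer who follows the text obtains valid standard errors.

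It does not dispose of the point. Placeholders stand in for variable names, not for structure. Step 3 does carry a BY on imputation number, so its absence from Step 2 does not look like shorthand. The code also fixes seeds and options, which makes it a natural starting point for programming.

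A reader might infer that the code, run as printed, yields wrong standard errors for the primary result. The documents do not support that. Step 3 as printed reads a dataset with no imputation number, so it never reaches a pooled standard error. The large effect needs Step 3 redirected while Step 2 is left alone, more than 2% non-monotone points, and software that renumbers imputations over the stacked rows, which the documents do not describe. SAP 6.1.4 expects only a small amount of intermittent missingness. On the other side, SAP 6.2 expects visits missed because of COVID-19 and rules out remote IGA assessment.

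A reader might also infer that two features of Step 1 damage the primary endpoint: treatment is absent from its model, and the code has rounding but no bounds. They barely touch it. The variable list ends at the Week 12 score, so a missing Week 12 is always trailing and is imputed in Step 2, whose model includes treatment and pooled site. The missing bounds are still a mismatch with the 0-4 limit in the text.

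**Conclusion.** The point holds as a contradiction between code and text, with a conditional effect; it is not a demonstrated error in the primary analysis. The conditional size is as follows.

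- **More than 2% non-monotone points:** type I error of about 28-35% with 3 Step 1 datasets, or 47-60% with 10, against a nominal 10%.
- **2% or less:** the missing BY is harmless. XX = 1 in Step 2 would make the standard error about 5-9% too small at 10-20% dropout.

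These figures assume that Step 2 is programmed as shown, that Step 3 is pointed at its output, and that the stacked copies share one imputation number. The correction should be made before unblinding.

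**What to change.** Amend SAP 6.1.4 as follows:

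1. Step 1: add `minimum=0 maximum=4` to match the text. State that XX (1, 3 or 10) applies to this step only, and reword the sentence after Step 2 accordingly.
2. Step 2: add a BY on the Step 1 imputation number, kept under its own name so that it is not overwritten, and set `nimpute=25`.
3. Build one identifier for each Step 1 by Step 2 combination, giving 25, 75 or 250 datasets.
4. Step 3: run PROC FREQ on data derived from the Step 2 output, BY that identifier and visit. Visit must stay, because the table shells report every visit.
5. Optional: bring treatment into Step 1, for example BY treatment. This is a small modelling improvement, not a correction.

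Leave the 1/3/10 table and the 25-to-250 statements in SAP 6.1.4 and 8.1.1 as they are. Moving the 25 imputations into Step 1 would be valid in itself, but it would contradict both. The cost is a few lines of pseudo code and one sentence, with no change to data collection or sample size.
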